4.5 Prohibited Concomitant Therapy

Unless there is a need for urgent intervention, additional medication for pain control or treatment of constipation (other than their maintenance opioid regimen and approved opioid medication for breakthrough pain) will not be allowed without prior approval from the principal investigator. This includes over-the-counter treatments for constipation and pain.

Unless defined as part of the usual care treatment arm, prohibited laxatives will include the

following:

- Milk of magnesia
- Magnesium citrate
- Non-absorbable phosphate
- Cascara sagrada
- Castor oil/mineral oil
- Epsom salt
- Lactulose
- Docusate
- Enemas (see Section 4.4 for exception to use)
- Tegaserod
- Lubiprostone (Amitiza®)
- Drugs blocking fat absorption with an associated laxative effect
- Prucalopride
- Prune juice
- Herbal preparations for constipation
- Bulk laxatives, such as psyllium and methylcellulose
- Any agent that is used in an off-label fashion to treat constipation (eg, colchicine, misoprostol, erythromycin, cholinesterase inhibitors such as donepezil)
- Any experimental constipation therapy

Prohibited medications include metoclopramide given its 5HT₄ agonism at the stomach causing promotility.

Opioid antagonists and mixed agonists/antagonists are also prohibited during study participation, which includes the following:

- Pentazocine
- Buprenorphine
- Nalbuphine
- Naloxone and other naloxone containing products, such as oxycodone/naloxone combinations (Targin®)
- Naltrexone and other natrexone containing products such as morphine/naltrexone combinations (Embeda®)
- MethylNaltrexone (Relistor®)
- Alvimopan (Entereg®)

Naloxegol is a sensitive substrate of CYP3A4 enzyme and a substrate of P-gp transporter, and CYP3A4 is the major CYP enzyme responsible for the metabolism of naloxegol. Concomitant use with strong CYP3A4 and/or P-gp inhibitors, moderate CYP3A4 and/or P-gp inhibitors, and/or strong CYP3A4 inducers are prohibited during study participation. Please see **Appendices B and C** for a list of these medications.

Anticancer therapy (chemotherapy, biologic or radiation therapy, and surgery) may be given to patients during study participation.

4.6 Adverse Drug Reactions, Dosing Delays/Dose Modifications

From initial treatment period to end of study visit, participants will be evaluated for possible toxicities that may have occurred during the previous treatment phase or drug dispensing cycle. Any patient who receives treatment on this protocol will be evaluable for toxicity. Severity of all adverse events will be evaluated according to the NCI CTCAE v4.03. Dose adjustments will be based on the naloxegol-related toxicity experienced during a treatment phase or newly encountered at the start of each treatment phase or drug dispensing cycle. Dose adjustments should be made according to the system showing the greatest degree of adverse event severity. If a patient experiences multiple adverse events and there are conflicting recommendations, the investigator should use the recommended dose adjustment

that reduces or delays the dose to the greatest degree. The participant may continue on therapy if the toxicity can be managed according to the dose modification guidelines as outlined below.

A separate 12.5 mg tablet will be available for study participants who develop more severe GI adverse events. For study drug compliance the pharmacy will indicate the date, dosage and quantity of drug dispensed. The subject will also maintain a the patient study drug diary (see sections 5.1.13.1 and section 8.1.2) that will be reviewed along with study drug counts to ensure that all missed doses or dose changes have been documented.

Patients requiring a delay of ≥ 2 weeks in initiation of study participation or requiring more than 2 dose adjustments during the course of naloxegol therapy will require authorization from the principal investigator to continue study participation.

Table 1: Dose Modifications for Naloxegol-Related Nausea and/or Vomiting

Vomiting	Management for Naloxegol
\leq Grade 1	No action required.
Grade 2	Hold until \leq Grade 1. Resume at same dose level.
Grade 3	Hold until $<$ Grade 2. Resume at reduced dose (12.5mg tablet).
Grade 4	Off protocol therapy
Recommended management: Dopamine antagonist antiemetic	

Table 2: Dose Modifications for Naloxegol-Related Diarrhea

Diarrhea	Management for Naloxegol
\leq Grade 1	No action required.
Grade 2	Hold until \leq Grade 1. Resume at same dose level.
Grade 3	Hold until $<$ Grade 2. Resume at reduced dose (12.5mg tablet).
Grade 4	Off protocol therapy
Recommended management: Loperamide antidiarrheal therapy, 4 mg at first onset, followed by 2 mg with each loose motion until diarrhea-free for 12 hours (maximum dosage: 16 mg/24 hours). Adjunct anti-diarrheal therapy is permitted and should be recorded when used.	

Table 3: Dose Modifications for Naloxegol-Related Abdominal Pain

Abdominal Pain	Management for Naloxegol
\leq Grade 1	No action required.
Grade 2	Hold until \leq Grade 1. Resume at same dose level.
Grade 3	Hold until $<$ Grade 2. Resume at reduced dose (12.5mg tablet).
Grade 4	Off protocol therapy

Table 4: Dose Modifications for Other Naloxegol-Related Toxicity

Grade	Management for Naloxegol
\leq Grade 1	No action required.
Grade 2	Hold until \leq Grade 1. Resume at same dose level.
Grade 3	Hold until $<$ Grade 2. Resume at reduced dose (12.5mg tablet).
Grade 4	Off protocol therapy

Dose Modifications for Renal Impairment

If a participant's renal function becomes compromised during the course of treatment with naloxegol, defined as GFR < 60 mL/min/1.73m², the naloxegol dose will be reduced to 12.5 mg tablet once daily.

Rare cases of GI perforation associated with the use of other peripheral opioid antagonists in OIC have been reported to occur shortly after initiation with drug and appear to be more commonly reported in patients with multiple co-morbidities, particularly those that might impair the local or global structural integrity of the GI tract.

Any at-risk patient who reports progressive or persistent severe abdominal pain should be evaluated immediately by their physician or referred for urgent medical assessment, especially in the presence of other symptoms such as fever, malaise or mental status changes.

4.7 Duration of Study Treatment

In the absence of treatment delays due to adverse events, treatment may continue up to a total 16 weeks (treatment periods including optional extension) or until:

- Inter-current illness or worsening of a medical condition that prevents further administration of treatment
- Unacceptable adverse event(s)
- Rescue therapy for patient's constipation fails secondary interventions and/or the investigator believes that other treatment options may be more beneficial
- The investigator believes that study treatment is jeopardizing patient safety
- Patient decides to withdraw from the study, **OR**
- General or specific changes in the patient's condition render the patient unacceptable for further treatment in the judgment of the investigator.

4.8 Duration of Follow Up

Patients will be followed for occurrence of adverse events for 28 days after removal from treatment or until death, whichever occurs first. Patients removed from treatment for unacceptable adverse events will be followed until resolution or stabilization of the adverse event. Patients will be asked to return to clinic for an end of study visit within 28 days of the final dose of study treatment.

4.9 Discontinuation from Study Participation

Patients may be removed from study participation at any time or at the discretion of the investigator for any of the following reasons:

- The patient or legal representative withdraws consent to participate;
- The patient is lost to follow-up;
- The patient dies;
- The patient is non-compliant with study procedures;
- The investigator believes that study treatment is jeopardizing patient safety.

5.0 STUDY PROCEDURES

Refer to the study **Schedule of Events** for assessments to be performed.

All patients will be closely monitored for safety and tolerability throughout treatment and at the completion of study treatment.

5.1 Definitions of Study Assessments

5.1.1 Medical history

A complete medical, surgical and oncology history as well as history of OIC are obtained at screening. Any changes from Screening (e.g. worsening severity or abnormal findings) are considered to be adverse events (AEs).

5.1.2 Demographics

Demographic profile will include date of birth, sex, race, and ethnicity.

5.1.3 Review subject eligibility criteria

Review of eligibility criteria as described in Section 3 to ensure subject qualification for study entry.

5.1.4 OIC confirmation

Prior to randomization, patients will be asked to report the number of bowel movements and rate their stool quality (using BSS) they have had in the past week. In order to meet study eligibility, the patient must report ≤ 3 bowel movements, or their estimated percentage of hard and lumpy stools (BSS of 1 or 2) $\geq 25\%$ during the preceding week. OIC may be confirmed at any time during screening and prior to initial treatment period Day 1.

5.1.5 Concomitant medications

All concomitant therapy, including anticancer therapy, anesthetic agents, vitamins, homeopathic/herbal remedies, nutritional supplements, opioid medication use, over-the-counter analgesic medication use, rescue laxative use, and all other over-the-counter “as needed” (prn), received by patients from 3 days prior to Study Day 1 until 28 days after the last study dose will be recorded in the patient’s medical record. If a reportable adverse event deemed related to study intervention (see Section 7) occurs within 28 days after last study dose and the patient has not started a new treatment, recording of concomitant medications related to the treatment of that adverse event should continue until resolution of the adverse event.

5.1.6 Physical exam

A complete physical examination should include the evaluation of general appearance; evaluation of head, eyes, ears, nose, and throat (HEENT); and cardiovascular, pulmonary, abdominal, musculoskeletal, skin, lymph nodes, neurological, and genitourinary systems. Subsequent exams may be targeted as appropriate.

Changes from baseline abnormalities should be recorded at each subsequent physical examination. New or worsened abnormalities should be recorded as adverse events if clinically significant.

5.1.7 Vital signs and height

Vital signs should include temperature, pulse, and blood pressure and weight. Height will only be collected at screening.

5.1.8 Performance status

Performance status is evaluated by the Eastern Cooperative Oncology Group (ECOG) performance scale.

5.1.9 Adverse event assessment

Baseline assessment of subject status for determining adverse events. Adverse events will be assessed using NCI CTCAE v4.03. See Section 7 for Adverse Event monitoring and reporting.

5.1.10 Hematology

Complete blood count to include hemoglobin, platelets, total white blood cell count and differential.

5.1.11 Serum chemistries

Comprehensive metabolic panel (CMP) to include: albumin, alkaline phosphatase, total protein, ALT/SGPT, AST/SGOT, BUN, creatinine, electrolytes (sodium, potassium, calcium, chloride, bicarbonate), glucose, and total bilirubin.

5.1.12 Pregnancy test (females of child bearing potential)

See section 3.1 for definition.

5.1.13 Patient-Reported Measures

All patient-reported measures will be completed via paper format, with materials provided to the patient by a study team member. A study member will provide initial training to the patient on how to complete study-required questionnaires and diaries. Patients are to complete the questionnaires and diaries in a quiet area, without assistance from family, friends or study team members. Patients must be able to read and comprehend the questionnaire in the language presented, and will be translated into foreign languages as needed for patient recruitment. Patients must complete the questionnaires prior to any interventions or discussions regarding their OIC with the investigator or study team members.

5.1.13.1 Patient Study Drug Diary

Patients will complete a daily study drug diary (**Appendix D**) during the period of time that they are receiving naloxegol: initial treatment phase for patients randomized to Arm A, crossover treatment phase for those randomized to Arm B; extension phase for all patients who choose to continue receiving naloxegol for an additional 12 weeks following the crossover phase. Participants will be asked to complete this diary even on days when a naloxegol dose was missed. The study drug diary will be reviewed with the patient during each visit to clinic, and a copy will be collected by a member of the study team. This diary will be used in combination with a pill count by the study team to support drug accountability.

5.1.13.2 Patient Medication Use Diary

Patients will complete a daily medication use diary as a record of all oral and self-administered medications received during the initial and crossover treatment periods (**Appendix E**). This includes any vitamins, homeopathic/herbal remedies, nutritional supplements, opioid medication use, over-the-counter analgesic medication use, rescue laxative use, and all other over-the-counter “as needed” (prn) medications. A copy of the medication use diary will be collected from the patient by a member of the study team during each visit to clinic and entries will be recorded on the concomitant medications case report form.

5.1.13.3 Patient Bowel Movement Diary

Patients will complete a daily bowel movement diary as a record of the number of daily bowel movements during the initial and crossover treatment periods (**Appendix F**). Participants will be asked to complete this diary even on days where no daily bowel movement has occurred. A copy of the bowel movement diary will be collected from the patient by a member of the study team during each visit to clinic.

5.1.13.4 Bristol Stool Scale (BSS)

Subjects will rate stool consistency through completion of the Bristol Stool Scale (BSS) after each bowel movement. The BSS was developed by Heaton at the University of Bristol and was first published in the Scandinavian Journal of Gastroenterology in 1997 (Lewis and Heaton 1997). It is a medical aid designed to classify feces into seven categories (**Appendix G**), as follows:

- 1 - Separate hard lumps, like nuts (hard to pass)
- 2 - Sausage-shaped, but lumpy
- 3 - Like sausage, but with cracks on its surface
- 4 - Like a sausage or snake, smooth and soft
- 5 - Soft blobs with clear cut edges (passed easily)
- 6 - Fluffy pieces with ragged edges, a mushy stool
- 7 - Watery, no solid pieces

Subjects will be asked to document a BSS score at the time of OIC confirmation and daily during the initial and crossover treatment periods. This score takes approximately 1 minute to complete.

5.1.13.5 PAC-SYM Questionnaire

The PAC-SYM questionnaire¹² (**Appendix H**) will be used to assess patient quality of life. The PAC-SYM questionnaire is a 12-item questionnaire that evaluates the severity of symptoms of constipation in 3 domains (stool, rectal, and abdominal symptoms) on a 5-point Likert scale ranging from 0 (absent) to 4 (very severe) in the 7 days prior to assessment. The items of the instrument were developed through literature review and patient interviews. The PAC-SYM has been extensively validated for constipation and is available in several languages. The translations into local languages have been performed according to a linguistic validation process. The PAC-SYM is validated for a **7-day recall**, therefore, participants will be asked to complete this questionnaire every 7 days during the initial and crossover treatment periods, every 28 days during the optional extension phase and at the end of study visit. This questionnaire takes approximately 5 minutes to complete.

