5.1.13.6 PAC-QOL Questionnaire

The PAC-QOL questionnaire¹³ (**Appendix I**) will be used to assess patient quality of life. The PAC-QOL questionnaire is a 28-item self-report instrument designed to evaluate the burden of constipation on patient's everyday functioning and well being in the 2 weeks (14 days) prior to assessment. Each item is rated on a 5-point Likert scale ranging from 0 (not at all) to 4 (extremely). Development of the PAC-QOL items was informed by both clinician and patient focus groups and the primary validation study evaluated use of the PAC-QOL in the US, Netherlands, Belgium, Canada, and Australia using French and Dutch translations in addition to the original English language based instrument.¹³ This questionnaire takes approximately 5 minutes to complete. The instrument can be used to generate an overall score, but is also reported to assess 4 specific constipation-related domains, including: 1) worries and concerns (11 items), 2) physical discomfort (4 items), 3) psychosocial discomfort (8 items), and 4) satisfaction (5 items). The PAC-QOL is validated for a **2-week recall**, therefore, participants will be asked to complete this questionnaire every 14 days during the initial and crossover treatment periods, every 28 days during the optional extension phase and at the end of study visit. This questionnaire takes approximately 5 minutes to complete.

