5.3 Procedures During Initial Treatment and Crossover Treatment Phases

During the initial and crossover treatment phases of the study, physical exam, ECOG performance status, vitals, weight, and laboratory tests will be performed on the first day of each treatment period. Thereafter, these procedures will be performed according to routine frequency for the participant's oncology care. If these procedures are performed as part of routine oncology care, results will be collected for the study.

5.3.1 Day 1, Day 18

- Documentation of concomitant medications, adverse events and serious adverse events
- ECOG performance status assessment
- Physical exam, vital signs, and weight
- Complete blood count with differential and platelets
- Comprehensive metabolic panel
- Naloxegol dispensing (*Arm A, Day 1 only; Arm B, Day 18 only*)
- Naloxegol administration (*Arm A, Day 1; Arm B, Day 18*)
- Patient study drug diary (*Arm A, Day 1; Arm B, Day 18*)
- PAC-SYM
- PAC-QOL
- BPI-sf
- BSS
- Patient medication use diary
- Patient bowel movement diary

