5.3.2 Days 2-7, Days 9-14, Days 19-24 and Days 26-31

- Documentation of concomitant medications, adverse events and serious adverse events
- Naloxegol administration (*Arm A, initial period only; Arm B crossover period only*)
- Patient study drug diary (*Arm A, initial period only; Arm B crossover period only*)
- BPI-sf
- BSS

- Patient medication use diary
- Patient bowel movement diary

5.3.3 Day 8, Day 25

- Documentation of concomitant medications, adverse events and serious adverse events
- Naloxegol administration (*Arm A, initial period only; Arm B crossover period only*)
- Naloxegol pill count (*Arm A, initial period only; Arm B crossover period only, via phone if in-person visit not conducted*)
- Patient study drug pill diary (*Arm A, initial period only; Arm B crossover period only*)
- PAC-SYM
- BPI-sf
- BSS
- Patient medication use diary
- Patient bowel movement diary

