5.4.1 Days 32-116 (Daily)

- Documentation of concomitant medications, adverse events and serious adverse events
- ECOG performance status assessment (*Day 32 only*)
- Physical exam, vital signs, weight (*Day 32 only*)
- Complete blood count with differential and platelets (*Day 32 only*)
- Comprehensive metabolic panel (*Day 32 only*)
- Naloxegol dispensing (*Day 32 only*)
- Naloxegol administration
- Patient study drug diary

5.4.2 Days 32, 39, 46, 53, 60, 67, 74, 81, 88, 95, 102, 109 (Weekly)

In addition to daily assessments listed in Section 5.5.1, the following will be performed:

- Naloxegol pill count (*via phone if in-person visit not conducted*)
- PAC-SYM (*Days 32, 60, 88 only*)
- PAC-QOL (*Days 32, 60, 88 only*)
- BPI-sf (*Days 32, 60, 88 only*)

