Appendix H. Patient Assessment of Constipation Symptoms (PAC-SYM)¹⁵

PAC-SYM ©

PATIENT ASSESSMENT OF CONSTIPATION ©

This questionnaire asks you about your constipation in the **past 2 weeks**. Answer each question according to your symptoms, as accurately as possible. There are no right or wrong answers.

For each symptom below, please indicate **how severe** your symptoms have been during the **past 2 weeks**. If you have not had the symptom during the past 2 weeks, check 0. If the symptom seemed mild, check 1. If the symptom seemed moderate, check 2. If the symptom seemed severe, check 3. If the symptom seemed very severe, check 4. Please be sure to answer every question.

How severe have each of these symptoms been in the last 2 weeks?	Absent 0	Mild 1	Moderate 2	Severe 3	Very severe 4
1. discomfort in your abdomen					
2. pain in your abdomen					
3. bloating in your abdomen					
4. stomach cramps					
5. painful bowel movements					
6. rectal burning during or after a bowel movement					
7. rectal bleeding or tearing during or after a bowel movement					
8. incomplete bowel movement like you didn't "finish"					
9. bowel movements that were too hard					
10. bowel movements that were too small					
11. straining or squeezing to try to pass bowel movements					
12. feeling like you had to pass a bowel movement but you couldn't (false alarm)					

English (USA) PAC-SYM Version 2.1-Sd (12-item, Standard version)
PAC-SYM © 1999 Mapi Research Trust, All rights reserved

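### PAC-SYM is scheduled weekly because of a 7-day recall, but the Appendix H form asks about the past 2 weeks, so Day 8 and Day 25 scores take in days before the current treatment

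*Combined protocol and SAP*

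**What the plan says.** Section 5.1.13.5 says PAC-SYM rates symptom severity "in the 7 days prior to assessment", calls it validated for a 7-day recall, and concludes that "participants will be asked to complete this questionnaire every 7 days during the initial and crossover treatment periods". Section 4.1 also lists it as a weekly assessment. During the two treatment periods, the Schedule of Events and Sections 5.3.1 and 5.3.3 place it on Days 1, 8, 18 and 25. Section 5.4.2 adds Day 32, but only for patients who enter the optional extension. Section 5.5 adds the end-of-study visit, after treatment.

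The form cited for this purpose, in Appendix H, refers to 2 weeks in its introduction, its instructions and its item header. The header asks "How severe have each of these symptoms been in the last 2 weeks".

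PAC-QOL follows the same logic without the conflict. Section 5.1.13.6 gives a 2-week recall, "therefore, participants will be asked to complete this questionnaire every 14 days during the initial and crossover treatment periods", and the Appendix I form also says 2 weeks. PAC-QOL is not listed for Days 8 and 25.

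Section 5.1.13 says "A study member will provide initial training to the patient on how to complete study-required questionnaires and diaries", but names no recall period. Section 9.3.3 analyses PAC-SYM with an ordinal logistic mixed model that has a treatment term and a categorical time effect for period. It does not say which PAC-SYM visits belong to which period.

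**The concern.** The protocol sets the frequency of each questionnaire from its recall period. A form with 2-week wording removes the stated reason for giving PAC-SYM every 7 days. In a crossover with 14-day periods, a mid-period score on that form looks back past the start of the current treatment. At Day 8 it reaches into the time before any study treatment. At Day 25 it reaches through the washout into the other treatment.

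The period term in Section 9.3.3 cannot correct this, because the mixing sits inside each score. Period 2 is the more exposed. Day 18 is completed on the first crossover day and looks back on period 1 and washout. Day 32 exists only for patients who extend. For a patient who declines the extension, Day 25 is the only PAC-SYM score taken after crossover treatment starts and before it ends. At stake is a diluted treatment comparison on this secondary endpoint.

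**Working it through.** The plan gives no figure of its own here, so the check is a count of recalled days against the calendar.

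**Inputs.** Treatment runs on Days 1–14 and 18–31 (regimen table, Section 4.1), with washout on Days 15–17. PAC-SYM visits are Days 8, 18 and 25, plus Day 32 for patients who extend. Recall is 7 days (Section 5.1.13.5) or 14 days (Appendix H). The visit day itself is left out, since Section 5.1.13.5 speaks of the days before assessment.

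**Formula.** Share of the true effect kept = (days on the treatment being scored − days on the opposite treatment) ÷ recall length. Pre-treatment and washout days count as 0, each recalled day has equal weight, and the scale is treated as linear. Day 18 is scored toward period 1.

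| Visit | 14-day recall covers | Share kept | 7-day recall covers | Share kept |
|---|---|---|---|---|
| Day 8 | 7 pre-treatment + 7 current | 7/14 = 0.500 | 7 current | 1.000 |
| Day 18 | 11 period 1 + 3 washout | 11/14 = 0.786 | 4 period 1 + 3 washout | 4/7 = 0.571 |
| Day 25 | 4 opposite + 3 washout + 7 current | (7 − 4)/14 = 0.214 | 7 current | 1.000 |
| Day 32 | 14 current | 1.000 | 7 current | 1.000 |

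**Visit day counted instead.** With 14-day recall, Day 8 has 6 pre-treatment and 8 current days (8/14 = 0.571). Day 25 has 3 opposite, 3 washout and 8 current days ((8 − 3)/14 = 0.357).

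**Period-adjusted contrast.** This is (mean share in period 1 + mean share in period 2) ÷ 2. Day 18 takes a negative sign if it is assigned to period 2. Without Day 32 there are four allocations (period 1 visits | period 2 visits):

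| Allocation | 14-day form | 7-day form | Change |
|---|---|---|---|
| 8 \| 25 | (0.500 + 0.214)/2 = 0.357 | 1.000 | −64% |
| 8, 18 \| 25 | (0.643 + 0.214)/2 = 0.429 | 0.893 | −52% |
| 8 \| 18, 25 | (0.500 − 0.286)/2 = 0.107 | 0.607 | −82% |
| 18 \| 25 | (0.786 + 0.214)/2 = 0.500 | 0.786 | −36% |

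If Day 32 were available for every patient, seven further allocations run from 56% smaller (8 | 18, 25, 32: 0.321 against 0.738) to 14% larger (18 | 32: 0.893 against 0.786).

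**Check on the remedy.** A score at the end of Day 14 or Day 31 recalls only current-treatment days under either wording (14/14 or 7/7), so its share is 1.000.

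**The case against.** The contradiction and the nominal day counts are not in dispute. The case against concerns the size.

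- **Counting convention.** Leaving out the visit day gives the larger loss. Counting it raises the retained share from 50% to 57% at Day 8 and from 21% to 36% at Day 25. This stands as a sensitivity, but the mixing remains.
- **Visit windows.** The Schedule of Events allows ±3 days. If the visit moves and the other dates do not, the 14-day form at Day 25 keeps anything from (4 − 7)/14 = −21% on Day 22 to (10 − 1)/14 = 64% on Day 28. A 7-day form is not immune: on Day 5 or Day 22 it keeps 4/7 = 57%. The 100% benchmark therefore needs a visit that is not early relative to the start of treatment. If the start day moves with the visit, the counts do not change.
- **Day 32.** Sections 2.4 and 6.4 confine this endpoint to the first 4 weeks of study treatment, and Day 32 is scheduled only for extension patients. On that reading the Day 32 allocations drop out, including the one where the 2-week form does better. This stands, and it leaves the four reductions of 36–82%.
- **Conditional harm.** Dilution requires that the printed form is used and that patients rate the whole 2 weeks. Staff could tell patients to think of the past week, but no section says so. It would also contradict a form that repeats the 2-week period and that Section 5.1.13 has patients complete without help from the study team.

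In one respect the 2-week form does better: at Day 18 it is less diluted by washout (3 of 14 days against 3 of 7).

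**Conclusion.** The inconsistency is certain: Section 5.1.13.5 and the form it cites give different recall periods, and no other text resolves them. With the printed form at nominal days, half of the Day 8 window and half of the Day 25 window fall outside the current treatment, and 4 of the 14 days at Day 25 are on the opposite one.

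The percentages are less certain. They assume equal day weights, nominal dates and a linear scale, and they are not the ordinal logistic estimate of Section 9.3.3. No single net figure follows until that section assigns visits to periods. Over all 11 allocations the contrast with the 2-week form runs from 82% smaller to 14% larger than with a 7-day form.

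This should be fixed, but its reach is limited to PAC-SYM scores. The primary feasibility endpoint, the daily bowel diary, BSS and BPI-sf data, and PAC-QOL do not carry this mismatch.

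**What to change.** Make Section 5.1.13.5, the Schedule of Events and Appendix H agree on one recall period. The documents alone cannot settle which.

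- **If 7 days:** replace the Appendix H form with one that has 7-day wording, and keep Days 8 and 25.
- **If 2 weeks:** take the comparison scores at the end of Days 14 and 31, leave Days 8 and 25 out of the treatment comparison, and align the weekly statement in Section 4.1 and the lists in Sections 5.3.1–5.3.3.

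In either case, state in Section 9.3.3 which PAC-SYM days belong to which period. If scores have already been collected, record which form was used and interpret Days 8 and 25 accordingly.

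A separate point, not caused by the form: Day 18 follows the washout under either recall, so an end-of-period score at Day 14 would avoid washout days.

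**Cost.** An IRB-approved amendment under Section 10.8. The 7-day option also needs a 7-day version of a copyrighted form, possibly with a licence, and the documents do not show that one is available. The 2-week option leaves one PAC-SYM score per period for the comparison. Neither needs more patients or clinic visits, since Days 14 and 31 are already paper-diary days.
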